#### 4.1.1 Algorithm for Calculating the Primary Implementation Outcome Measure

Two FDA-approved treatments for OUDs that can be provided in medical settings and documented in EHRs are included as OUD treatment. Buprenorphine and injectable XR naltrexone use will be determined from medication orders (EHR data) and procedures (EHR for all health systems and claims data for 2 health systems). Text string searches on generic and brand medication name will be used to ascertain buprenorphine formulations indicated for OUD treatment (sublingual, tablet, film, subdermal implants, and subcutaneous) and injectable XR naltrexone use from medication orders. A clinical co-investigator then reviews all hits on the text string search as part of quality control. Procedure codes will also be used to identify injectable formulations, implants, and oral formulations given in the office setting. Pharmacy dispensings are the gold standard for outpatient non-injectable medication use but they are not comprehensively available for 5 of the 6 health systems (whereas medication orders are routinely available in all 6 health systems). These 4 health systems are not insurers and therefore do not receive claims from outside pharmacies. Site (health system) principal investigators state that patients frequently obtain medications from pharmacies outside of the health system.

A single medication order or procedure code for buprenorphine formulations indicated for OUD treatment or injectable XR naltrexone (the latter with an OUD diagnosis) will be considered OUD treatment, though sensitivity analyses will examine this assumption (Section 5.2.4)

The algorithm for calculating the primary outcome measure of days on OUD medication (buprenorphine or injectable XR naltrexone) is as follows with details in Appendix A.

Ascertained from the EHR and claims as specified above, all buprenorphine and naltrexone XR injections will be quality checked, combined, cleaned and values imputed (as necessary), and collapsed into an episode or episodes (if gaps in use) of OUD treatment.

Episodes of OUD treatment will then be summed to calculate the total patient days covered with OUD treatment in the time-period of interest. Details on estimating episodes of treatment and summing episodes are in Appendix A but briefly they will be estimated as follows from variables

commonly available in the EHR – medication orders (i.e., medication name, date ordered, form, quantity, strength, strength unit, number of refills, and directions for use [SIG]) and procedures (medication name, form, strength, strength unit, and date administered).

Specifically, we will do the following:

- 1) Perform quality checks for outlier/implausible values for variables required to calculate the outcome and impute outliers/implausible values and missing values. See Appendix A for further details.
- 2) Estimate days' supply for orders of buprenorphine film and sublingual tablets.
  - a. Translate directions for use (SIG) into pills per day (PPD). For example, "Take 1 pill twice a day" is a PPD=2.
  - b. Divide the quantity field by PPD to estimate days' supply. Add any additional day's supply from refills on the original order to estimate the total days' supply of the order. For example, an order with quantity=60, PPD=2, and refills=2 would have a day's supply=90.
- 3) Assign naltrexone injection and buprenorphine subcutaneous Sublocade a day's supply=28.
- 4) Assign Probuphine (implant) a day's supply=180. Assign Brixadi a day's supply of 7 or 28 depending on the product.
- 5) Estimate runout dates (date when the medication supply provided runs out) as order/procedure date plus days' supply. An order (or dispensing in secondary measures for sensitivity analyses) on 1/1/2018 with a day's supply = 15 is estimated to runout on 1/15/2018.
- 6) Prior to dropping injectable XR naltrexone orders or procedures, we will describe patients with both OUD/OD and AUD diagnosis codes and adjudicate if needed
  - a. For patients with 1+ injectable naltrexone orders or procedures and both 2+ OUD/OD and 1+ AUD diagnoses, provide a table of the numbers of OUD/OD and AUD diagnoses in 2 years pre-randomization and a similar table for post-randomization users of naltrexone.
  - b. Adjudicate subjects with both 2+ OUD/OD and 1+ AUD diagnosis codes to decide whether to include or exclude as OUD treatment, using the number of times a code was used from 7a.
  - c. Drop remaining injectable XR naltrexone if OUD diagnosis criteria are not met:
    - i. Drop injectable XR naltrexone in the pre randomization period if there are not 2+ visits with an OUD/opioid overdose (OD) diagnosis (can be 1 OUD and 1 OD code) in the pre randomization period.
    - ii. Drop naltrexone injections in the post randomization period if there are not 2+ visits with an OUD/OD diagnoses (can be 1 OUD and 1 OD code) in the pre or post randomization period.
- 7) In the pre and post-randomization periods, create continuous use episodes defined as OUD treatments with gaps  $\leq 7$  days between the runout of one order/procedure and the start date of the subsequent (other cut points to be evaluated in sensitivity analyses after summarizing the distribution of gaps). For example, two OUD treatment episodes with treatment episode 1 start 1/1/2018 and runout 1/15/2018 and treatment episode 2 starting 1/17/2018 and runout 2/5/2018 are rolled into one episode of continuous treatment (start

1/1/2018 and end 2/5/2018). In general, this gap applies to same medication orders/procedures and different medications.

- a. One exception is that gaps of  $\leq 14$  days between the runout of a buprenorphine order and subsequent naltrexone XR injections are allowed in defining continuous use episodes to account for required washout periods prior to naltrexone XR injection.
- 8) Pre and post randomization episodes are not allowed to overlap. They will be left and right censored accordingly. For example, a treatment episode of 90 days with 15 days in the post randomization period (includes randomization date) will be split into two episodes with one episode contributing 75 days of treatment pre-randomization and a second episode contributing 15 days of treatment post randomization.
- 9) Add the number of days of each continuous use episode to arrive at total days of OUD treatment in the distinct periods of pre-randomization and post-randomization. The algorithm does not allow for double counting of any overlapping orders or procedures.

#### **4.2 Definition of Objective 2 Effectiveness Outcome Measure (Powered Secondary Outcome)**

The primary effectiveness (Objective 2) endpoint is a person-level count measure of the number of days of acute care utilization in the follow-up period, among patients with an OUD diagnosis pre-randomization. This measure includes visits to urgent care clinics or emergency departments (EDs), as well as days hospitalized. Acute care utilization will be determined from the EMR and insurance claims data when available.

For hospitalizations, the number of inpatient days will be the number of days from admission to discharge, inclusive. For urgent care or ED (referred to collectively as “emergency care”), each unique date with a visit to an urgent care or ED will be counted as 1 day (even if the patient stays overnight), except in the uncommon event that an ED visit spanned 3 or more days ( $< 0.5\%$  of ED records collected in Data Pull 4, including both randomized and non-recruited UPC clinics), in which case the encounter will be classified as a hospitalization (as patients may be boarded in an ED until a hospital bed becomes available and some are subsequently discharged from the ED if no hospital bed ever became available). If a patient is admitted from urgent care or an ED, the ED or urgent care day is not (double) counted when counting the number of days of acute care.

##### **4.2.1 Addressing Data Anomalies and Outliers**

In examining the hospitalization data during interim Data Pulls, a few data anomalies were discovered (e.g., extremely long hospitalizations). Records with an anomaly will first be manually reviewed by health system study staff and corrected (where possible) or handled as follows:

- Discharge dates before the admission date: We assume the dates were incorrectly reversed and switch them back ( $< 50$  records in Data Pull 4 out of over 300,000), unless the resulting length of stay is an outlier (identified by comparing to the distribution in the full sample), in which case a basic imputation approach will be applied (defined below).
- Missing discharge date: most hospitalization records with a missing discharge date were embedded within another hospital record; after removing these and collapsing across any overlapping records,  $< 0.5\%$  of the remaining  $\sim 275,000$  hospitalization records (in Data Pull 4) had a missing discharge date. For these records length of stay will be imputed (details below).

In addition, hospital records with long inpatient stays ( $\geq 180$  days) will be manually reviewed by the health system to determine whether there may have been a data error.

**Imputation approach:** For the rare scenarios with data anomalies, we will impute the median length of stay based on inpatient episodes among patients within the same health care system (HCS), stratified by whether the patient had any OUD diagnosis during the study period.

### 4.3 Definitions of Secondary Measures

Additional secondary measures will be analyzed to describe outcome measures reflecting processes of care, implementation, and effectiveness. The following table describes each of the measures that will be examined either descriptively, or through formal modeling, as described in the statistical analysis section below. Measures will be calculated broadly in the full study sample to facilitate analyses across different study samples. For example, we will calculate the number of days of OUD medication treatment for each patient, which will be summed across patients as part of the primary Objective 1 outcome and will also be analyzed at a patient-level among patients with an OUD diagnosis pre-randomization. Other implementation measures (e.g., number of patients treated) will be analyzed in both the full study sample of all patients with a visit, as well as in the subsample of these patients who had an OUD diagnosis pre-randomization.

**Table 2: Primary, Secondary, and Other Outcomes Measured During Post-Randomization Period Based on EHR Data (\*measures from clinicaltrials.gov)**

Outcome Measures

*Objective 1. Patient-days of OUD medication treatment (primary outcome). Clinic-level number of patient-days of OUD treatment with buprenorphine and XR-NTX documented in the EHR during the period from randomization until two years after, reported per 10,000 PC patients in the clinic in the two years post-randomization.

*Objective 2. Acute care utilization (secondary outcome). Patient-level number of days of acute care utilization during the period from randomization until two years after, among patients with an OUD diagnosis documented in the EHR in the three years prior to randomization.

Other Outcome Measures of Implementation

*Newly diagnosed OUD (Implementation Reach). Clinic-level number of patients with a new International Classification of Disease (ICD) code for OUD documented in the EHR during the period from randomization until two years after who did not have an OUD diagnosis documented in the EHR in the three years prior to randomization, reported per 10,000 patients in the PC clinic in the two years post-randomization.
 
This measure will also be estimated for any OUD diagnosis (new and previous diagnoses).


*Initiation§ of OUD treatment (Implementation Reach). Clinic-level number of patients who initiate: (1) buprenorphine or (2) XR-NTX with an indication of OUD as documented in the EHR during the period from randomization until two years after, reported per 10,000 PC patients in the clinic in the two years post-randomization.
 
This measure will also be estimated for any OUD treatment (initiation and on-going treatment).
 
§Initiation of buprenorphine and XR-NTX in the context of PROUD trial outcome measures refers to the first order for OUD medication treatment post-randomization with no treatment with these medications in the prior 365 days (including pre-randomization). See Section 4.1.1. for operationalization of OUD in this context.

**Buprenorphine daily dose of 16 mg or more (Implementation Reach).** Clinic-level number of patients on  $\geq 16$  mg per day of buprenorphine at any time during the period from randomization until two years after randomization as documented in the EHR, reported per 10,000 PC patients in the clinic in the two years post-randomization.

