Modification: We would like to modify Appendix A, Table 5 and Table 8 in the protocol to align all three of these sections with the data being collected weekly by the NCMs. The NCM weekly reporting elements in these sections are slightly different than what is being collected for the trial. Below is an outline of weekly data reports being collected by the NCMs for the trial and sent to the TA Team (with the Implementation Monitoring Team (IMT) being cc'd).

- # Screened
- # Intakes*
- # New starts*
- # Follow-ups seen on scheduled day*
- # Walk-ins seen
- # Re-engagements seen
- # Naltrexone injections given
- # Buprenorphine injections given
- # Discharges and reason (screened only but never started, completed, administrative/non-adherence, incarceration, transferred to higher level of care, medical, lost to follow up, deceased, other)*
- # No shows
- # Visits rescheduled
- # Patients seen new to primary care clinic
- # New patients seen with primary care outside health system

- # Patients transferred from elsewhere already on medication*

* by oral buprenorphine, injectable buprenorphine, oral naltrexone, injectable naltrexone

Summary of differences: Appendix A, Table 5, and Table 8 indicated that we captured number of patients with unexpected positive urine drug tests and those contacted within 7 days, however those data are not collected. Appendix A and Table 5 had not mentioned that we captured information on: # no shows; most of the above bullet points are broken out by groups: oral buprenorphine, injectable buprenorphine, oral naltrexone, injectable naltrexone; number of patients transferred to NCM who were already on medication (broken out by medication); # of walk-in patients seen (broken out by medication). In addition, Appendix A and Tables 5 and 8 did not indicate that we captured data on patients being treated with injectable buprenorphine and oral naltrexone.

Rationale: As the trial launched and the NCMs began reporting data, the reporting elements for the NCM weekly report were adjusted slightly to ensure the most relevant data were being collected in relation to the standards of care for treating OUDs in primary care. These adjustments were made as a part of the TA Team process, supported by formative evaluation between the TA Team and the IMT.

Modification #17 (Date: 11/16/2020)

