### 3.0 STUDY POPULATION

Patients are eligible for inclusion in the trial if:

- 1) they had a PC visit at a PROUD trial PC clinic in the pre-randomization and/or follow-up period (defined above), and
- 2) age is 16 to 90 years at the time of a PC visit during the study period.

Eligible PC visits refer to outpatient clinic visits (in which the patient was age 16 to 90 on the day of the visit) to the departments of adolescent and pediatric medicine (including teen clinics), family practice, geriatric, general practice, or internal medicine that are provided by a physician, physician assistant, nurse practitioner, resident or fellow with one of these specialties.

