#### **5.5.1 Rationale for Conducting Analyses Within a Secondary Sample**

It is expected that some of the patients who initiate treatment in PROUD intervention clinics will have been diagnosed with OUDs after randomization, potentially due to the PROUD intervention. It is also possible that patients may be newly attracted to the clinic (or to the health system entirely) potentially because of the PROUD intervention (based on the fact that at least 77% of patients treated in MA were new to the clinic after implementation). The primary analysis of Objective 2 described above would miss any impact of the PROUD intervention on both of these subsamples of patients, because they were not identified pre-randomization (because they were not previously diagnosed with OUDs or because they did not visit the clinic in the pre-randomization period). These secondary analyses within the secondary Objective 2 study sample, which includes patients seen in the trial clinics with an OUD diagnosis post-randomization only, are designed to capture these additional patients who may be affected by the PROUD intervention.

On the other hand, these secondary analyses must account for the fact that patients with newly recognized OUD in the PROUD intervention clinics post-randomization are likely to differ markedly from patients with newly recognized OUD in the UPC clinics post-randomization. Further, it is likely that these patients could differ in ways that may be associated with acute care utilization (e.g., patients could be referred for ongoing buprenorphine treatment from an ED or hospital that started treatment). To address this, analyses will adjust for covariates known or hypothesized to be associated with acute care utilization (based on prior literature), as well as secondarily for any additional covariate observed to differ across patients with newly recognized OUD post-randomization in the UPC versus PROUD intervention clinics.

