#### For each week

- # of New starts
- # of Re-engagements
- # of Transfers (patients new to NCM who were already on treatment)
- # of Discharges

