## 8.0 OTHER CONSIDERATIONS

### 8.1 Missing Data

Given that the primary and secondary outcomes rely on the EHR data or insurance claims data, if there is no evidence of a particular event, such as provision of buprenorphine or a visit to the ED, we will assume that the event did not occur. These same assumptions apply to the only covariate in the primary analyses of the primary Objective 1 and Objective 2 measures (baseline value of the respective measure in the 2 years prior to randomization).

Our primary Objective 1 outcome uses medication orders to capture days of OUD medication treatment as orders were available for all health systems and dispensings are considered incomplete at 5 of the 6 health systems. However, because dispensing data and not medication orders are considered the gold standard, we will conduct sensitivity analyses in which we estimate the primary outcome at each health system using only medication dispensing data in the 3 health systems that have some dispensing data and pharmacies in both the usual care and intervention clinics (Section 5.2.4).

For Objective 2, given our visit-based sample we are not able to identify when a patient is no longer observable. To address this, we will conduct a sensitivity analysis for our Objective 2 outcome among the two health systems that are health insurance plans in which we use enrolled samples (Section 5.4.3). We will also conduct sensitivity analyses that restrict to patients with evidence of being active in the health system post-randomization (as described above in Section 5.4.2).

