f Prescribers determined from medication orders in the electronic health records. Providers assigned to clinics based on number of visits with patients in the clinic post-randomization.

Abbreviations: NCM – nurse care manager; ITT- intent to treat; OUD: opioid use disorder; SD – standard deviation; XR-NTX – extended release injectable naltrexone

Supplemental Table 1a is the main Table 1a above by health system
Supplemental Table 1b is the main Table 1b above by health system
Supplemental Table 2 is the main Table 1a above but using data for the post randomization period and among patients with an eligible visit post randomization (closest to study end as anchor for variables)
Supplemental Table 3 is the main Table 2 above by health system

Supplemental Table 4 is the main Table 2 above with OUD treatment related outcomes stratified by newly initiated treatmenta versus on-going treatmentb, and the OUD diagnosis outcome stratified by newly diagnosed OUDc versus prevalent OUDd.
 
a OUD treatment in the 2 years post randomization and no OUD treatment in the prior 365 days
 
b OUD treatment post-randomization that does not meet criteria for initiated above
 
c 1+ OUD diagnosis anywhere in the health system in the 2 years post randomization and no OUD diagnosis in the 2 years pre randomization.
 
d 1+ OUD diagnoses in both the 2 years pre randomization and 2-years post randomization

Supplementary Table 5. Sensitivity analyses focused on assumptions made in estimating patient-years of OUD medication treatment, clinic-level results in the 2 years post randomization			
	Patient years treatment /10,000 patients seen in clinic post-randomizationa		Mean difference (95% CI)b
	6 intervention clinics	6 usual care clinics	
Primary outcome			---
Limited to the time period in which the NCM started seeing patients d			
Limited to health systems that successfully implement the MA model e			
Covariate adjusted c			
Using a combination of medication orders and pharmacy dispensings			
Adding Methadone Maintenance Therapy data from 1-2 sites, per 10,000 patients seen in the 1-2 clinics post randomization			
Adding pharmacy dispensings and MMT data at the 1-2 sites with these sources of data			

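### The initiation outcome has a 365-day washout but does not require the patient to be observable in the health system during it, so patients arriving from outside already on treatment count as new starts

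*SAP*

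**What the plan says.** SAP section 4.3, Table 2, defines initiation for all trial measures as the "first order for OUD medication treatment post-randomization with no treatment with these medications in the prior 365 days (including pre-randomization" period. Supplemental Table 4 in SAP 10.1 repeats the rule for its newly initiated stratum: "OUD treatment in the 2 years post randomization and no OUD treatment in the prior 365 days". Table 7 of the same section uses it too.

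Three other provisions decide what an empty 365-day window means:

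- **Sample entry (SAP 3.0).** Patients are eligible if "they had a PC visit at a PROUD trial PC clinic in the pre-randomization and/or follow-up period" and they meet the age criterion. One visit during follow-up is enough.
- **Source of treatment data (SAP 4.1.1).** Buprenorphine and XR-naltrexone use "will be determined from medication orders (EHR data) and procedures (EHR for all health systems and claims data for 2 health systems"). Dispensings enter only in sensitivity analyses.
- **No record (SAP 8.1).** Where there is no evidence of an event "such as provision of buprenorphine or a visit to the ED, we will assume that the event did not occur".

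The documents also recognise patients who arrive already treated. Protocol Modification #16 lists "Patients transferred from elsewhere already on medication" among the weekly nurse care manager (NCM) report items, apart from new starts. SAP 7.3 keeps a weekly and cumulative number "of Transfers (patients new to NCM who were already on treatment").

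**The concern.** For a patient with no earlier contact with the HCS, the 365-day window is empty because nobody was recording, not because the patient was untreated. The definition cannot tell the two apart. Moving an existing course of treatment into the HCS is then counted as improved reach.

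The measures built on initiators inherit the problem. Retention at 80% of days, 6-month retention and discontinuation are all counts of initiators per 10,000 clinic patients. Each outside transfer who stays on treatment adds one to a retention count, and each who stops for 60 days or more adds one to discontinuation. Initiation and 80% retention are marked in SAP Table 2 as ClinicalTrials.gov measures.

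Inflow need not be equal by arm. Protocol 3.2.3.1 expects the Massachusetts model to bring new patients into primary care. SAP 5.5.1 cites experience that "at least 77% of patients treated in MA were new to the clinic after implementation", expects newly recognised patients to differ markedly between arms, and mentions referral for buprenorphine already started in an ED or hospital. Adjusting for the clinic's baseline value cannot remove an inflow that begins after randomization.

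**Working it through.** **Step 1: apply the rules to one patient.** Suppose a patient has been treated by an outside prescriber, has never been seen in the HCS, and receives a first HCS order on study day 200. One follow-up visit admits the patient (SAP 3.0). The look-back window runs from day −165 to day 199. It contains no HCS order or procedure (SAP 4.1.1), so it is read as untreated (SAP 8.1), and the patient is an initiator (SAP 4.3). A patient whose earlier order or procedure is in HCS records within the window is classed as ongoing. The gap therefore concerns treatment that HCS records do not hold.

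**Step 2: look for a planned analysis that corrects the count.**

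| Provision | What it covers | What it leaves |
|---|---|---|
| SAP Table 2, any-treatment measure and retention in all subjects | Avoids the new/ongoing split | Does not correct the initiation count |
| SAP 5.2.5 | Splits patient-days by clinic and diagnosis history | Not initiation |
| SAP 7.4 | Describes treated patients by arm, including those not seen in the HCS before randomization | Descriptive; initiation not re-estimated |
| SAP 7.5 | Describes treatment elsewhere within the HCS before the first NCM visit | Not treatment outside the HCS |
| SAP 4.3, 5.6 and Objective 2 Table 2 shell | Initiation among patients with OUD and a trial-clinic visit before randomization | A subsample; not the clinic-level outcome |

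None re-estimates clinic-level initiation without patients who lack an observable look-back.

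**Step 3: possible size.** The documents give no expected initiation rate, so there is no plan figure to reproduce. Let S be the share of apparent starts in patients new to the HCS, and t the share of those already treated elsewhere. Neither is given; both are assumptions here. The nearest figures are at least 77% new to the clinic (SAP 5.5.1) and 7–30% existing clinic patients, hence 70–93% new to the clinic (Protocol 3.1.7). New to the clinic is not new to the HCS, so S = 0.77 serves as a high-side value.

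Misclassified share = S × t; apparent/true starts = 1/(1 − S × t).

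| S | t = 10% | t = 20% | t = 30% | t = 50% |
|---|---|---|---|---|
| 0.25 | 2.5% | 5.0% | 7.5% | 12.5% |
| 0.50 | 5.0% | 10.0% | 15.0% | 25.0% |
| 0.77 | 7.7% | 15.4% | 23.1% | 38.5% |

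Protocol 7.1.1 plans about 75–225 inductions per intervention clinic. With S = 0.77 and t = 10%, 75 × 0.077 = 5.8 and 225 × 0.077 = 17.3, so about 6–17 would be transfers. With t = 30%, 75 × 0.231 = 17.3 and 225 × 0.231 = 52.0, so about 17–52.

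**Step 4: effect on the comparison.** With a true arm ratio of 1 and the same t in both arms, the apparent ratio is (1 − S_UPC × t)/(1 − S_PROUD × t).

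| S_PROUD, S_UPC | t = 10% | t = 20% | t = 30% | t = 50% |
|---|---|---|---|---|
| 0.77, 0.77 | 1.00 | 1.00 | 1.00 | 1.00 |
| 0.77, 0.50 | 1.03 | 1.06 | 1.11 | 1.22 |
| 0.77, 0.25 | 1.06 | 1.12 | 1.20 | 1.42 |
| 0.25, 0.10 | 1.02 | 1.03 | 1.05 | 1.09 |

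For example, (1 − 0.25 × 0.3)/(1 − 0.77 × 0.3) = 0.925/0.769 = 1.20. The UPC shares are also assumed.

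**The case against.** The best defence is that the outcome does what it says: it counts starts as documented in the EHR, reach means patients receiving the desired care, and attracting new patients is an intended mechanism. The any-treatment measure does not depend on the new/ongoing distinction. The main results shell (Objective 1, Table 2) shows any treatment and has no initiation row; the split appears in Supplemental Table 4 and Table 7. The Objective 2 Table 2 shell estimates initiation in a sample that excludes everyone new to the HCS. Protocol 11.5 already asks for caution with secondary outcomes.

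Much of this stands, and it limits the point. It does not make a relocated course of treatment an initiation, and the registered clinic-level count remains without a check.

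Several stronger readings are tempting but unsupported:

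- *There is no look-back.* There is one, of 365 days. What is missing is a requirement of observability during it.
- *All transfers become new starts.* Transfers with an HCS order or procedure in the window are classed as ongoing.
- *The excess falls mainly in PROUD.* That is a reasonable expectation, not a finding. No UPC share is given, and UPC clinics may improve OUD care as they choose (SAP 1.2.2).
- *The NCM log gives the true number.* It counts patients new to the NCM who were already treated, including those treated within the HCS, and exists only for intervention clinics.

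**Conclusion.** The concern holds in a limited form. The initiation definition cannot separate untreated patients from patients whose treatment was not recorded in the HCS, and no planned analysis corrects the clinic-level initiation count or the retention and discontinuation counts built on it. If PROUD clinics draw more patients already treated elsewhere, initiation and retention counts are biased in their favour; discontinuation counts may move against them. With equal shares by arm there is no bias in the ratio.

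The size is unknown. The illustrated range, 2.5% to 38.5% of apparent starts and an apparent ratio of 1.00 to 1.42 under no true difference, rests entirely on assumed shares. A reader might take the 77% as the share at risk of misclassification. It is the share new to the clinic in Massachusetts, not the share new to the HCS or already on medication. The primary outcome, patient-days of treatment, does not use this definition and is unaffected.

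**What to change.** Keep the registered initiation and retention counts as defined. Add to Supplemental Table 4 a sensitivity analysis by arm, parallel to SAP 5.5.4.a, reporting initiation, and retention among initiators, separately for:

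- (a) patients with any HCS visit, diagnosis or procedure (or enrolment, where available) at least 365 days before the first order;
- (b) patients without that look-back, labelled *first HCS-documented treatment, prior treatment unknown*.

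State that the registered count will be interpreted in light of whether row (a) agrees with it. Report NCM transfer counts only as context for the intervention arm, since they include transfers within the HCS.

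The cost is SAP wording and a small code change; no new data are needed. Row (a) has two limits. It leaves out genuine new starters who are new to the HCS, a group the model aims to attract, which is one reason not to let it replace the registered count. And one earlier contact does not guarantee continuous observability: SAP 5.4.2 acknowledges that a visit-based sample does not show when a patient has gone elsewhere.
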